the same hydration metrics - blood pressure (BP), weight, and ultrafiltrate volumes - using home monitoring equipment (BP cuff, body weight scale, and hanging scale). The no-app group will manually enter the information into their “PD logbook”- the handwritten paper booklet which is usual care. In contrast, the app group will automatically collect and enter the same information into the CKD-PD app using NFC technology on their smart phone. It will be displayed in the CKD-PD app for the patient and uploaded to the CKDNET database in the Thai Care Cloud; it then can be viewed on the CKD-PD web application by the PD clinic staff. Patients will monitor their hydration status on a graphical display on their smartphone. PD clinic staff will be notified daily about “action required” alerts on the web application. For example, systolic BP greater than 140 mmHg, diastolic BP greater than 90 mmHg, weight gain greater than 3% based on dry weight, or ultrafiltrate volume < 500 milliliters will trigger a response from the PD clinic. Nephrologists will make clinical interventions to treat OH according to standard practice in Thailand, which include BP and diuretic medication adjustments, change in diet or fluid intake, dialysis prescription adjustments or referral for urgent clinical evaluation. Clinical interventions can occur at unscheduled patient contact (e.g. patient call) or scheduled patient contact (routine clinic visit) Our primary outcome measure will be the incidence of clinical interventions for OH, both routine and urgent, in 1 year from enrollment. Secondary outcome measures include OH related complications, hospitalizations and deaths, and will be collected from PD clinic and hospital records, and the CKDNET database.

Setting and study population: The study will be conducted at the PD clinics at Srinagarind Hospital (N=100) the academic referral hospital affiliated with Khon Kaen University, Khon Kaen Hospital (N=50) the government referral hospital for Khon Kaen province, and Chaiyaphum Hospital (N=50), the government referral hospital for the neighboring Chaiyaphum province in northeast Thailand. We will recruit 200 patients with end-stage renal disease on PD from KKH to achieve a total sample size of 160.

Inclusion criteria are

- patients with CKD from any cause on home based peritoneal dialysis
- age ≥ 18
- access to a smartphone capable of running the CKD-PD app
- ability of the patient or surrogate to demonstrate successful use of the CKD-PD app

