Inclusion of children: We will enroll patients 18 years of age or older. The prevalence of PD in patients in Thailand under 18 years of age is <1% [8], therefore making it difficult to include this age group in our study. In addition, the etiologies of chronic kidney disease and co-morbidities are different in children and PD is used less frequently in children compared to hemodialysis.

Collaborating sites: None

Statistical Design and Power: We determined our sample size by using the difference in incidence rates between two Poisson means with 25% precision. Data collected from Srinagarind Hospital indicate the intervention rate for OH, based on current practice of patients contacting the PD clinic staff with symptoms or concerns of OH outside of scheduled appointments, to be 4 times/week in 91 patients or a mean intervention rate of 2.3 times/patient-year. Assuming a two-fold increase in the mean event rate for patients using the CKD-PD app or

4.6 times/patient-year in the CKD-PD app group, the desired sample size is 80 patients for each group, using a two-sided, large-samples z-test of the Poisson event-rate difference at a significance level of 0.05. Allowing for a 10% dropout rate, we will recruit a total of 200 patients (100 in each group). Our assumption that use of CKD-PD app will result in a twofold increase in the incidence of clinical interventions is based on our preliminary experience with the 42 patients currently using the CKD-PD app. In those 42 patients, especially those with unstable fluid and blood pressure control, the app frequently identifies outlier measurements resulting in intervention opportunities which are not possible in the no-app control group.

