addition to training on how to use other features on the CKD-PD app including self-monitoring of hydration metrics and in-app communication with PD staff. The no-app group will receive instructions on how to record the same information in their paper PD log book as well as information about how to contact the clinic by phone. Research staff will also make a home visit for app-group participants at the start of data collection to confirm correct equipment set up and use.

Clinical interventions: In both the app and no-app groups, clinical interventions for OH can occur at either an unscheduled patient contact (e.g. phone call, clinic visit, or emergency visit) or at a scheduled clinic visit. In the app group, clinical interventions can also occur when an action required notification occurs, and the PD clinic staff contacts the patients and determines that a change in treatment is indicated to manage the OH. This occurs when a patient is flagged as an outlier (action required) because one or more of the hydration metrics is outside of the established acceptable range (see paragraph directly below). The PD clinic staff, after reviewing the patient's hydration metrics, will initiate contact with the patient, to review hydration metrics and patient symptoms. If the PD nurse confirms abnormal hydration metrics (action required) or clinical symptoms consistent with OH, the case will then be referred to the nephrologist to review the information and determine the need for a clinical intervention. Nephrologists will make clinical interventions according to standard practice in Thailand, summarized as guidelines and provided to nephrologists and PD clinic staff for reference at the beginning of the study. An episode of clinical intervention is defined as treatment intervention for abnormal hydration metrics or clinical symptoms of OH with 1 or more changes in patient management: change in medications, dialysis prescription, fluid or salt restriction, or urgent clinic/hospital visit. A contact that results in no change in management is not considered a clinical intervention for OH.

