2. *Clinical intervention for overhydration:* Change in medical treatment in response to OH detected by clinical symptoms or hydration metrics. Interventions may include a change in medications to treat OH such as anti-hypertensives or diuretics, dialysis prescription, dietary sodium/fluid restriction, referral for evaluation in clinic, or hospitalization. This information will be collected in the electronic PD clinic study log at the time of the clinical intervention.
3. *Unscheduled clinic contacts:* When patients in either group make an unscheduled contact with the PD clinic this will be recorded in the PD clinic electronic study log. Unscheduled clinic contact can also occur in the “app” group when PD clinic staff contact a patient in response to abnormal hydration metrics. Unscheduled contacts include any phone call, text, social media, or web app message, and unscheduled visit to the PD clinic or emergency department. The information collected included patient name/MR#, reason for contact, mode of contact, who initiated contact, date and time of day, and action taken. Unscheduled clinical interventions will be recorded at the time of the event.
4. *Scheduled clinic contacts:* Patients in both groups will have regularly scheduled clinic visits, typically bimonthly. Clinical interventions for OH made during this visit will be recorded in the electronic PD clinic study log. A medical record review will also occur at each visit to collect any other hospitalizations, complications, or clinical interventions that may have occurred in the interim.
5. *CKDNET database review:* In order to ensure all events have been captured, we will review the CKDNET database, which has all inpatient and outpatient visits, on a bimonthly basis.

Data collection overview

Data elements for analysis of covariates at enrollment: These will include: age, sex, educational level, cause of CKD, eGFR, co-morbidities (e.g. diabetes, hypertension, albumin level), previous hospitalizations for OH, smoking status, distance from clinic, months on PD, months of CKD-PD usage, and app user type (patient or surrogate). The source will be medical records and patient interview at time of enrollment.

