Clinical interventions used: We will record the type of clinical intervention, patient symptom/hydration metric abnormality, whether it was occurred from a scheduled or unscheduled communication, and ordering clinician. This information will be recorded in an electronic study log at time of PD clinic visit, or time of communication to patients.

Outcome measures: Our primary outcome measure will be the incidence of clinical interventions for OH in 1 year from enrollment. Secondary outcome measures include OH-related complications

Drop out/Lost to follow up: The number of patients who drop out, are lost to follow up or died during the study period will be collected. This information will be collected from chart reviews and PD clinic communications and recorded in the electronic clinic study log.

PD clinic/patient communications: We will also collect data about communications between PD clinic staff patients or their surrogates by logging phone calls and messaging app contacts. This information will include who initiated the call, whether or not it resulted in a clinical intervention, the type of clinical issue, and mode of communication. This information will be recorded in the PD clinic electronic study.

Potential risks to participants: This study poses low risk to participants with regard to physical, psychological, social, cultural or legal aspects as both groups receive the same standard of care as currently provided to PD patients at the study site nephrology clinics, including routine clinic appointments, medications, dialysis prescriptions, dietary recommendations, educational and other community support networks, and urgent services e.g. phone contact to PD clinic, unscheduled clinic visits, and emergency care. We have identified some potential specific risks including data breaches, lost or malicious hacking of computers, loss of privacy, concern about change or access to PD care, over or under identification of overhydration, failure to detect life threatening outlier data points in a timely fashion, technology failure, communication failures and errors, and unintended consequences of using a new technology. Strategies to mitigate these risks are discussed below. Alternative strategies available to participants are the option to decline or withdraw from the research at any time.

Informed Consent and Assent

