3. *We anticipate that CKD-PD app users will receive increased number of clinical interventions as a result of increased monitoring.* We believe this result will improve effectiveness and quality of care, however there is always inherent risk in any clinical intervention even if the benefits are determined to outweigh them. All clinical decisions will be made by the same providers already caring for the patients, according to the usual standard of care. Study clinicians will receive training for interpreting CKD-PD app data

which includes a summary of the local standard of practice, assessing the whole clinical picture, and looking at data trends rather than single isolated readings.

4. *CKD-PD app users may introduce new source of potential error by incorrect data entry.* Patient or surrogate will be given training in proper data entry techniques and observed in their homes to make sure they can use app correctly.
5. *Failure of technology (loss of network connection, malfunction of smart phone) could result in unanticipated delay or loss of data for CKD-PD app users.* We will provide participants in the CKD-PD app group with directions on how to respond to failure of technology. This includes resuming use of the PD logbook and how to notify study staff in the event of technology failure or question on correct use of CKD-PD. This inadvertent data loss is similar to a lost log book in the control group.
6. *CKD-PD app users are at risk for potential unexpected or unintended consequences of introducing a new process or technology.* Study staff will be monitoring the use of CKD-PD, looking for potential issues or problems that were unexpected or unanticipated throughout the study including mismatched expectations among MDs, RNs, and patients.
7. *Loss of confidentiality and or privacy due to loss of data or hardware.* Privacy and confidentiality loss may occur due to data breaches, physical loss or theft of computers, or carelessness of study personnel. We will minimize these threats by using password enabled and encrypted computers, de-identified data where possible, and research ethics training for study participants. The CKDNET and Thai Care Cloud has data safety features built in to its foundational structure including firewalls, encryption, and access restrictions.

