The knowledge gained from this research is important for several reasons. First, determining whether or not using the CKD-PD app can result in earlier treatment for OH is important before scaling up the intervention to a larger population. Second, the information gained from this research is important preliminary information in order to conduct the research of greatest interest – whether or not use of the CKD-PD app can reduce complications and hospitalizations and decrease mortality for PD patients. If proven successful, this can meaningfully impact the lives of thousands of PD patients and potentially reduce costs. Third, this research will also provide information about whether or not PD patients can successfully self-monitor their hydration status, which is valuable knowledge affecting further implementation of the CKD-PD app to a larger population. Fourth, it will also provide the opportunity to link patient collected mobile health data with hospital and clinic records to provide a rich multi-modal database for predictive analytics. Considering these benefits to individual participants and other PD patients, the risks are reasonable

Monitoring and Quality Assurance

Our project measures the impact of the CKD-app on managing OH. Our intervention is the use of the app, not a specific medication or treatment and all participants will receive the same clinical interventions based on the same usual standard of practice. Therefore, we feel there is low risk to patients as the care and treatment of patients is

standardized- the difference is the timeliness of the interventions. Because our research will introduce a technology that can impact the frequency of clinical interventions and the quality of data used to manage patients, we have outlined several ways to reduce or manage the potential risks. In addition, we will take the following steps to ensure safety.

1. Develop guidelines for PD clinic staff regarding the process of monitoring and response to the daily outlier alerts generated by the CKD-PD web application, and communications from patients or surrogates. These guidelines will provide details on the daily review of hydration metric alerts for “action required”, action steps to be taken (e.g. contact patient, review with nephrologist), recording in study log.

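### The sample size is planned on overhydration interventions outside scheduled visits, but the primary outcome also counts those made at scheduled visits

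*Combined protocol and SAP*

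**What the plan says.** Statistical Design and Power (Aim 2) sizes the trial on the difference between two Poisson rates with 25% precision. The control rate is 4 interventions a week in 91 patients, or 2.3 per patient-year, "based on current practice of patients contacting the PD clinic staff with symptoms or concerns of OH outside of scheduled appointments". It is doubled to 4.6 for the app group, giving 80 patients per group.

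The Aim 2 Overview defines the endpoint more widely: "Our primary outcome measure will be the incidence of clinical interventions for OH, both routine and urgent, in 1 year from enrollment". The Clinical interventions paragraph says that in both groups interventions "can occur at either an unscheduled patient contact (e.g. phone call, clinic visit, or emergency visit) or at a scheduled clinic visit", and adds a route for one arm only: "In the app group, clinical interventions can also occur when an action required notification occurs". Planned research procedures, item 4, states "Patients in both groups will have regularly scheduled clinic visits, typically bimonthly" and has OH interventions made at those visits entered in the study log. The Outcome measures paragraph and the planned analysis do not restrict the count to unscheduled contacts. For each intervention the study records "whether it was occurred from a scheduled or unscheduled communication" (Clinical interventions used).

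The plan describes the app's effect in two ways. The risk section says "We anticipate that CKD-PD app users will receive increased number of clinical interventions as a result of increased monitoring". Monitoring and Quality Assurance says of the two arms that "the difference is the timeliness of the interventions".

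**The concern.** The planning rate and the endpoint count different events. Under usual care the bimonthly visit is where the nephrologist reviews the logbook and assesses hydration, so treatment changes made there may form a sizeable part of the control-arm count. The 2.3 leaves them out, and no scheduled-visit rate appears anywhere in the plan.

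Two things are at stake. First, the precision claim is the stated justification for 80 per group, and it has not been shown for the endpoint that will be analysed. Second, if the app moves some treatment forward from the next scheduled visit to an alert-triggered contact, one scheduled intervention disappears as one unscheduled intervention appears. The total count does not change, although treatment was earlier, and earlier treatment is the trial's research question.

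**Working it through.** **Inputs from the plan.** Control rate r0 = 2.3 and app rate r1 = 4.6 per patient-year; two-sided 5% level; 25% precision; 80 per group; one year of follow-up; bimonthly visits, so about six a year.

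**Assumed, because the plan gives no value.** S is the rate of scheduled-visit OH interventions per patient-year, range 0 to 6. The upper end would need a treatment change at every visit. R is the number of extra between-visit interventions per patient-year that replace scheduled ones; its values are illustrative. Variance is pure Poisson and every patient completes a year.

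**Formulas.** SE = √((r0 + r1)/n). Half-width HW = 1.96 × SE. Power = Φ(d/SE − 1.96), with d = r1 − r0.

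**Reproducing the plan's figures.**
- Control rate: 4 × 52/91 = 2.29.
- Precision target: 0.25 × 2.3 = 0.575.
- n = 1.96² × (2.3 + 4.6)/0.575² = 80.2 per group.

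The arithmetic is right, but it rests entirely on the rates from outside scheduled visits.

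**A. S adds equally to both arms.** The difference stays at 2.3 and the variance term becomes 6.9 + 2S. For S = 3, HW = 1.96 × √(12.9/80) = 0.79, and 0.79/2.3 = 34%.

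| S | Rates | Ratio | HW, n = 80 | HW / difference, n = 80 | HW / difference, n = 90 | Power, n = 80 |
|---|---|---|---|---|---|---|
| 0 | 2.3 vs 4.6 | 2.00 | 0.58 | 25% | 24% | >99% |
| 1.2 | 3.5 vs 5.8 | 1.66 | 0.67 | 29% | 27% | >99% |
| 3 | 5.3 vs 7.6 | 1.43 | 0.79 | 34% | 32% | >99% |
| 6 | 8.3 vs 10.6 | 1.28 | 0.95 | 41% | 39% | >99% |

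The n = 90 column is 100 recruited per group less the stated 10% dropout. Setting and study population instead gives 160 in total, which is 80 per group.

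**B. The total rate doubles** (n = 80).

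| S | Rates | HW | HW / difference |
|---|---|---|---|
| 1.2 | 3.5 vs 7.0 | 0.71 | 20% |
| 3 | 5.3 vs 10.6 | 0.87 | 16% |
| 6 | 8.3 vs 16.6 | 1.09 | 13% |

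**C. Some extra interventions replace scheduled ones.** Control rate 2.3 + S, app rate 4.6 + S − R, so d = 2.3 − R. With S = 3 and n = 80:

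| R | Rates | Difference | HW | Power |
|---|---|---|---|---|
| 0.5 | 5.3 vs 7.1 | 1.8 | 0.77 | >99% |
| 1.0 | 5.3 vs 6.6 | 1.3 | 0.76 | 92% |
| 1.2 | 5.3 vs 6.4 | 1.1 | 0.75 | 82% |
| 1.5 | 5.3 vs 6.1 | 0.8 | 0.74 | 56% (61% at n = 90) |

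At S = 3, 80% power needs a difference of 1.07, so R = 2.3 − 1.07 = 1.23. That is 53% of the extra interventions, or 41% of the scheduled ones (1.23/3). The threshold moves with S. At S = 1.2, replacing every scheduled intervention (R = 1.2) still leaves power at 93%. At S = 6 power falls below 80% once R exceeds about 0.97.

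**The case against.** The strongest reply is that no harm to the sample size is shown. In A the power stays above 99%, in B precision improves, and only C loses material power, using two values the plan does not supply. The plan's main expectation is more interventions. The doubling is said to rest on opportunities the control arm does not have, and the sentence after the one on timeliness says the technology may affect how often interventions occur. S = 6 is a ceiling, since a contact with no change in management does not count.

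All of that stands, and it is why this is not a claim that the trial is underpowered. It does not remove the mismatch. The trial was sized on precision, and the 25% does not carry over to the wider endpoint under A, B or C. The twofold increase is worded as applying to clinical interventions in general, but it is applied to the 2.3 base, and the experience with 42 app users is cited without a rate.

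It can also be said that a shift to earlier treatment is what the app is meant to achieve, so a primary outcome restricted to between-visit interventions would be legitimate. That is arguable. But only the app arm has the alert route, so such a count would rise through timing alone even if no patient received more treatment. Keeping the sponsor's total count and showing the two components separately avoids this.

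Finally, the plan does not say that past scheduled-visit interventions can be retrieved. That is fair, and a stated range would serve instead.

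**Conclusion.** The concern holds. The 2.3 and 4.6 rates, the ratio of 2 and the 25% precision apply to interventions arising outside scheduled visits, not to the routine-plus-urgent count that is the primary outcome. The direction of the error is not fixed. At 80 per group, relative half-width runs from 29% to 41% if S between 1.2 and 6 adds equally to both arms, and from 20% to 13% if the total doubles. Power to exclude zero is threatened only if replacement is substantial: at S = 3, just over half of the extra interventions. These figures rest on assumed values of S and R, pure Poisson variance and complete follow-up; overdispersion would widen every interval. The point should be fixed, but it does not call for a larger trial.

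**What to change.** 1. Keep the all-intervention count as the primary outcome.
2. Take the scheduled-visit OH intervention rate from existing Srinagarind clinic records or, if it cannot be retrieved, state an assumed range.
3. Restate the control rate, expected difference, ratio and precision for that endpoint at 80 per group and at about 90 (100 less 10% dropout). Say whether the twofold increase applies to the total or only to between-visit interventions.
4. Pre-specify reporting of the arm difference separately for scheduled and for unscheduled or alert-triggered interventions, using the scheduled/unscheduled status already recorded. A shift towards earlier treatment is then visible.

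The cost is one look-up (if the records allow it), one recalculation and some added wording in the analysis plan. It needs no extra patients and no new data item. The stated precision may become less favourable.
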